#### 9.1.2.2 Day of Gene Transfer (Day 0)

The venue for gene transfer will be determined during the screening visit. There is a range of subject ages, from 6 months through age 14 years. For the youngest subjects, sitting still during the gene transfer (up to 90 minutes) may be problematic. For these youngest subjects, gene transfer will be performed in the hospital's Procedure Center under sedation, and they will be monitored in the Pediatric Intensive Care Unit after the gene transfer. For older subjects – anticipated to be any subject above the age of 3 years – the gene transfer will be performed within the Pediatric Intensive Care Unit itself, followed by monitoring in the same unit. Transfer out of the PICU may be undertaken after the initial 24 hours of post-infusion monitoring, if the SI has no concerns.

Prior to Gene Transfer, the following assessments will occur at this visit:

- Medical history
- Concomitant Medications
- Adverse Events
- Physical Assessment (physical exam will consist of the anesthesia evaluation prior to sedation or by the study team if sedation is not required))
- Vital Signs (temperature, respiratory rate, heart rate, and blood pressure)

*The following procedures work will occur at this visit:* 

- Picture of Injection Site, both prior to and after Gene Transfer
- Gene Transfer

The following samples will be collected for vector shedding studies 4 and 8 hours post gene transfer (see Section 10.4 for details):

- Blood
- Urine
- Saliva
- Feces

Prior to vector infusion, an assessment will be performed of vitals to be collected for clinical purposes by either anesthesia staff or the study team, depending on the planned use of anesthesia or not.

If sedation is required for subjects, they will continue on their usual diet until eight hours prior to gene transfer, after which they will have no solid food; clear liquids will be allowed up until two hours prior to gene transfer, after which they will be fully NPO. They will resume their usual diet after they have returned to pre-sedation baseline. The specifics of the gene transfer itself follow below. If no sedation is required, subjects will be allowed a normal diet until 2 hours prior to the gene transfer after which they will need to be fully NPO.

If the subject appears inadequately hydrated in the judgment of the SI, bolus(es) of 10-20 mL/kg normal saline may be given during the time between either admission or Procedure Center check-in and gene transfer.

If sedation is not required, the subject will become NPO 2 hours prior to gene transfer and will remain NPO for 2 hours after gene transfer is completed. D5 1/2NS will be infused in the second IV during the NPO period.

Gene transfer will be performed under sterile conditions within an appropriate inpatient facility. If deemed necessary by the SI, the gene transfer will occur under light to moderate sedation under the direction of a qualified anesthesiologist. If required, the subjects will be given sedation utilizing NCH anesthesia protocols that minimize the risk of anesthetic reaction in muscular dystrophy.

Sedation is being utilized in this instance to minimize anxiety or uncooperative behavior in the subjects, with an aim of maximizing potential study participation benefit to the pediatric subject by preventing study agent subcutaneous infiltration or IV loss with study agent spillage (the subjects will receive the *minimal efficacious dose* identified in the animal model). In those subjects who in the opinion of the SI (and in consultation with the anesthesiologist and parents) are determined to not need sedation in order to safely deliver the vector, sedation may be deferred, and the vector delivered in the PICU.

All subjects participating in this trial will receive an intravenous injection of scAAV9.U7.ACCA via peripheral limb vein. Dosing is the minimum efficacious dose as established in murine studies.

• 
$$n=1-3-3.0 \times 10^{13} \text{ vg/kg}$$

The total vector genome dose for subjects who weigh  $\geq 20 \text{kg}$  will be adjusted by rounding up to the closest whole kilogram. The total vector genome dose for subjects who weigh < 20 kg will be adjusted by rounding the subject body weight to the nearest tenth of a kilogram. Dosing is extrapolated from efficacy observed in preclinical studies as the minimal efficacious dose identified in the animal model.

Subjects will be closely monitored for side effects during the infusion, including continuous heart rate, respiratory rate, and pulse oximetry; and intermittent blood pressure monitoring. Heart rate, respiratory rate, pulse oximetry (only if sedation is being utilized), temperature, and blood pressure will be measured before and immediately after the infusion, and at least every five minutes during the infusion if sedated, and every 15 minutes if not sedated. Monitoring will be repeated at 15 minutes post-infusion, every 15 minutes for 4 hours following the infusion, and then every hour until transfer from the PICU to the Neurology floor. On the Neurology floor, vital signs will be measured every 4 hours until discharge.

Infusion reactions: Infusion will be terminated for evidence of an allergic reaction of **grade 2 or greater**, including anaphylaxis, based upon CTCAE v5.0 criteria, and reported using these criteria:

Grade 1: Transient flushing or rash, drug fever <38° C (<100.4° F); intervention not indicated

Grade 2: Rash, flushing, urticaria, dyspnea, drug fever >38° C: Intervention or infusion interruption indicated; responds promptly to symptomatic treatment (e.g., antihistamines, NSAIDS, narcotics); prophylactic medications indicated for ≤24 hrs

Grade 3: Prolonged (e.g., not rapidly responsive to symptomatic medication and/or brief interruption of infusion); recurrence of symptoms following initial improvement; hospitalization indicated for clinical sequelae (e.g., renal impairment, pulmonary infiltrates)

Grade 4: Life-threatening consequences; urgent intervention indicated

Grade 5: Death

Under CTCAE v5.0 criteria, anaphylaxis is by definition grade 3 (Symptomatic bronchospasm with or without urticaria; allergy-related edema/angioedema, hypotension), and would result in infusion termination and systemic treatment.

Subjects will remain in an independent hospital room following gene transfer and remain hospitalized for up to 48 hours post gene transfer.

#### 9.1.3 Post Gene Transfer Monitoring Plan

To facilitate these scheduled visits, all subjects will remain in the Columbus metropolitan area for a minimum of two weeks following gene transfer. If there is a systemic immune response that leads to acute respiratory distress syndrome, which implies a severe inflammation of the lung parenchyma, the subject would be hospitalized and treated aggressively with fluid replacement for hypotension if necessary and receive pulse methylprednisolone treatment (1 gram per day) over 3-5 days.

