## 6.4 Dosing plan

The proposed phase I/IIa clinical trial is an open-label single injection study of systemic (intravenous) delivery of scAAV9.U7.ACCA for DMD subjects with associated duplications of exon 2 in the DMD gene. Preclinical data shows that the small nuclear RNA (snRNA) construct delivered by the scAAV9.U7.ACCA vector causes significant skipping of exon 2, resulting in

exclusion of one (wild type) or both copies (Del2) of the exon from the mature messenger RNA (mRNA) with a high degree of efficiency. Translation of either the wild-type mRNA or N-truncated mRNA (via IRES translational initiation) results in a highly functional isoform. The dose selection is based on toxicology-biodistribution studies and predicted by pre-clinical studies in non-human primates.

This protocol is designed to deliver the vector via a one-time infusion through a peripheral vein of the DMD subjects. The subjects will receive the minimal efficacious dose (3 x  $10^{13}$  vg/kg) as identified in murine studies. The total vector genome dose for subjects who weigh  $\geq 20$ kg will be adjusted by rounding the subject body weight up to the closest whole kilogram. The total vector genome dose for subjects who weigh <20kg will be adjusted by rounding the subject body weight to the nearest tenth of a kilogram.

Dose (vg/kg)	N
$3.0 \times 10^{13}$	1-3

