#### 7.1 Inclusion/Exclusion

Inclusion Criteria

- 1. Age greater than 6 months and less than 14 years.
- 2. Confirmed duplication of exon 2 the DMD gene using a clinically accepted technique that completely defines the mutation.
- 3. Pre-ambulant (not yet walking) or ambulant (as defined by the ability to walk 10 meters without assistance).
- 4. Males of any ethnic group will be eligible
- 5. Ability to cooperate with muscle testing.
- 6. In subjects age 4 and above, stable dose and regimen of corticosteroid therapy (including either prednisone or deflazacort and their generic forms) for at least 12 weeks prior to gene transfer.

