- Total IgG
- D-Dimer\*\*
- Direct Bilirubin
- SC5b-9\*\*
- C3, C4\*\*
- CH50\*\*
- Antibody testing for Hepatitis B, C and HIV
- ELISA for detection of total antibodies to AAV9
- ELISpots for T-cell responses to AAV9 and Dystrophin
- Blood for vector shedding studies

\* For subjects taking drugs that potentially induce GGT synthesis through the cytochrome P450 system, the clinically significant range will be estimated starting at two times the levels obtained from the baseline screening test and up.

\*\* These laboratory tests have been recommended by the DSMB to be obtained at screening. These will not necessarily be exclusionary but having a baseline value will be helpful for comparison if a subject were to have any platelet or renal abnormalities that may be immune mediated after gene transfer.

The following urine lab work will occur at this visit:

- Urinalysis
- Urine for biobanking
- Urine for vector shedding studies

The following additional samples will be collected for vector shedding studies:

- Saliva
- Feces

For children under 10 kg in weight, the blood draw schedule will be reviewed to limit blood draw volumes to  $\leq 3\%$  of total body volume over a 24 hour period and  $\leq 10\%$  of total body volume over a 30 day period. The study team may deem it necessary to move or remove non-safety-related blood draws to other days if the volume drawn in one 24-hour period will be too near to 3% of total body volume.

Repeat testing of laboratory abnormalities within the screening period: Given the biologic variability inherent in some laboratory testing results, we will retest subjects with minimal and not clinically significant abnormalities resulting in values outside the NCH lab's normal range as defined by Table 7, such as minimal abnormalities of hemoglobin or CBC values. Similarly, subjects with anti-AAV9 endpoint titers at (but not above) the cutoff level of 1:400 will be retested for confirmation of titer. Normal values on the second of these tests will be considered to be acceptable for enrollment.

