#### 9.1.2 Gene Transfer Visit

#### 9.1.2.1 Pre Infusion Visit (Day -1)

Subjects will arrive at the Nationwide Children's Hospital within 24 hours prior to gene transfer.

The following assessments will occur at this visit:

- Medical history
- Concomitant Medications
- Adverse Events
- Physical Exam
- Vital Signs (heart rate, respiratory rate, temperature, blood pressure, height (see Section 10.5 for more details) and weight)

The following blood lab work will occur at this visit:

- Complete blood cell count (CBC) and differential, platelets
- Aspartate aminotransferase (AST)/alanine transaminase (ALT)
- Gamma-glutamyl transpeptidase (GGT)\*
- A Comprehensive Metabolic Panel (CMP) that includes:
  - o Albumin/Serum total protein
  - o Serum total bilirubin
  - Electrolytes
  - o Calcium
  - o Creatinine/Blood Urea Nitrogen (BUN)
  - o Serum glucose
  - Alkaline phosphatase
- Prothrombin time (PT)/activated partial thromboplastin time (PTT)/INR
- Creatine kinase (CK)
- Direct Bilirubin
- ELISpots for T-cell responses to AAV9 and Dystrophin
- Whole blood for biobanking

In previous gene therapy studies at NCH, there has been an observed antigen specific T-cell response to the AAV vectors. This is an expected response between 2 - 4 weeks following gene transfer. One possible consequence to such antigen specific T-cell responses is clearance of the transduced cells and loss of transgene expression. All subjects (ages 4 years and older) will already be on prednisone, prednisolone, or deflazacort for 12 weeks at time of enrollment as part of the inclusion criteria. The standard clinical dose of prednisone or prednisolone is 0.75 mg/kg/day, and the standard clinical dose of deflazacort is 0.9 mg/kg/day. In order to dampen the host immune response to our AAV-based therapy, for each subject the glucocorticoid dose will be increased to prednisone or prednisolone 1.0 mg/kg/day, not to exceed 60 mg/day; subjects on deflazacort at enrollment will be placed on prednisone or prednisolone for the immediate perinijection period. For subjects younger than 4 years of age who may not be on a corticosteroid,

\* For subjects taking drugs that potentially induce GGT synthesis through the cytochrome P450 system, the clinically significant range will be estimated starting at two times the levels obtained from the baseline screening test and up.

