- 15. For children under 10 kg in weight, the blood draw schedule will be reviewed to limit blood draw volumes to ≤ 3% of total body weight over a 24 hour period and ≤ 10% of total body weight over a 30 day period.

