# 10.6.1 Prophylactic Administration of Prednisone/Prednisolone

All subjects will be discharged from the hospital on oral prednisone or prednisolone at 1 mg/kg/day, which will be adjusted according to IFN-gamma T-cell studies in the following weeks. Subjects will also continue on a PPI until they return to their baseline corticosteroid dose or sooner based on the subject's symptoms and discretion of the sponsor investigator and/or parent.

If the **30 day** post-infusion IFN-gamma T-cell responses to AAV9 and dystrophin show ≤50 SFC per 1 x 10^6 PBMCs, the subject's prednisone or prednisolone dose will be decreased back to the standard clinical dose of 0.75 mg/kg/day. Those subjects who had been on deflazacort may be switched back to the standard clinical dose of 0.9 mg/kg day. For either regimen, approximations of these target doses may be allowed to account for pill formulations (for prednisone and deflazacort), as in clinical practice. If either the AST or ALT exceeds >2.5X the subject's baseline values, and results are confirmed on a follow-up blood test, the prednisone or prednisolone regimen will be maintained at 1 mg/kg/day until the enzyme levels fall within a range, 2.5X the baseline value. Subjects may be asked to undergo a weekly blood test outside of prescheduled visits should the SI deem it necessary to monitor the T-cell response or AST/ALT levels more closely.

If the IFN-gamma T-cell responses show  $\geq 50$  SFC per 1 x  $10^6$  PBMCs, we may increase the dose to approximately 2 mg/kg/day depending on T-cell response measured by ELISpot assay and prolong a subsequent tapering protocol based on the individual subject's immune response profile as assessed by subsequent ELISpot assays (as on the schedule above). Based upon other studies performed at NCH, we anticipate that oral prednisone or prednisolone may be administered for up to 120 days post gene transfer prior to the return to the standard clinical corticosteroid regimen of each subject.

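### The ARDS rescue pulse in Section 9.1.3 is a flat 1 gram per day of methylprednisolone, in a trial that enrols from just over 6 months of age and states every other steroid dose per kg

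*Combined protocol and SAP*

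**What the plan says.** Section 9.1.3 describes what happens if a systemic immune response leads to acute respiratory distress syndrome: the child is hospitalized, given fluids for hypotension if needed, and would "receive pulse methylprednisolone treatment (1 gram per day) over 3-5 days". No other section returns to this dose or scales it.

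The population is defined in Section 7.1: "Age greater than 6 months and less than 14 years", with pre-ambulant children eligible. Section 9.1.1 sets limits on blood volume that begin "For children under 10 kg in weight", and the Table 8 footnotes repeat the rule.

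Elsewhere the protocol doses by weight:

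- Section 9.1.2.1 gives background regimens of 0.75 mg/kg/day (prednisone or prednisolone) and 0.9 mg/kg/day (deflazacort). Around the infusion the dose is "increased to prednisone or prednisolone 1.0 mg/kg/day, not to exceed 60 mg/day".
- Section 10.6.1 discharges subjects on 1 mg/kg/day. For a raised T-cell response it adds that "we may increase the dose to approximately 2 mg/kg/day".
- Section 9.1.2.2 sets the hydration bolus per kg: "bolus(es) of 10-20 mL/kg normal saline may be given".
- Section 6.4 calculates the vector dose for subjects under 20 kg by "rounding the subject body weight to the nearest tenth of a kilogram".

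**The concern.** The largest steroid dose in the protocol is the only one not tied to body weight, and the age range runs from infancy to adolescence. A flat amount gives the smallest child the highest dose per kg. The protocol recognises body size as a safety matter for blood draws, hydration, vector and oral steroids, but not here.

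What is at stake is the safety of a critically ill child. No power, alpha or stopping-rule figure depends on this sentence. Safety is the primary outcome, however, and with one to three subjects a single child is between a third of the trial and all of it.

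**Working it through.** The documents do not derive the 1 gram figure, so there is nothing to reproduce. The check has two parts.

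**1. Basis of each stated steroid dose**

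| Section | Use | Dose | Basis |
|---|---|---|---|
| 9.1.2.1, 10.6.1 | Background prednisone or prednisolone | 0.75 mg/kg/day | per kg |
| 9.1.2.1, 10.6.1 | Background deflazacort | 0.9 mg/kg/day | per kg |
| 9.1.2.1 | Around the infusion | 1.0 mg/kg/day, maximum 60 mg/day | per kg, capped |
| 10.6.1 | At discharge | 1 mg/kg/day | per kg |
| 10.6.1 | Raised T-cell response | about 2 mg/kg/day | per kg |
| 9.1.3 | ARDS rescue pulse | 1 g/day for 3-5 days | flat |

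Section 10.6.1 allows approximation to suit pill formulations, but those doses remain weight-based.

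**2. The flat dose per kg**

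Daily dose per kg = 1000 mg / weight. Course dose per kg = 3000 to 5000 mg / weight.

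The protocol names 10 kg (blood-draw rule) and 20 kg (vector rounding rule) as thresholds. It gives no subject weights, so the other rows are assumptions chosen to show the range.

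| Weight | Source | mg/kg/day | Course, mg/kg |
|---|---|---|---|
| 7 kg | assumed | 1000/7 = 142.9 | 429-714 |
| 8 kg | assumed | 1000/8 = 125.0 | 375-625 |
| 10 kg | protocol threshold | 1000/10 = 100.0 | 300-500 |
| 20 kg | protocol threshold | 1000/20 = 50.0 | 150-250 |
| 40 kg | assumed | 1000/40 = 25.0 | 75-125 |
| 60 kg | assumed | 1000/60 = 16.7 | 50-83 |

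Between the two protocol thresholds the ratio is 100/50 = 2. Between the assumed extremes it is 60/7, about 8.6. The peri-infusion oral dose, by comparison, scales with weight: 10 mg/day at 10 kg and 60 mg/day at 60 kg, where its cap is reached.

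**The case against.** The strongest reply is that the documents contain no paediatric pulse dose, maximum or toxic threshold for methylprednisolone. From the text alone one can show that mg/kg rises as weight falls, which is true of any flat dose. One cannot show that 1 gram is wrong at a given weight. That stands, and it is why no toxicity claim is made and no replacement figure is offered. The arithmetic also concerns dose per kg, not exposure, since no pharmacokinetics are given.

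The comparators are different drugs used for background treatment or prophylaxis, and not everything in the protocol scales with weight: Section 8 sets a flat 20 mL flush. So the other per-kg doses do not prove the pulse wrong. They do show that the protocol normally doses steroids by weight and has a capped format ready to use.

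The sentence can also be read as an outline rather than an order, since it gives no volume or rate for the fluids. Intensive-care staff would probably scale the dose, and Section 15.1 permits departures in an emergency when the subject's care requires it. This lowers the likely harm. But the sentence does name a drug, a daily amount and a duration. Under Section 15.1 a scaled dose becomes a deviation from the protocol, and no alternative is supplied. Nor does the plan say where the child would be treated: subjects leave hospital on Day 2 and need remain in the Columbus area for only two weeks.

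Finally, the event is remote. It needs a very small child, immune-mediated ARDS and literal use of the figure, among at most three subjects. That bears on priority, not on whether the text is right.

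**Conclusion.** The concern holds. The rescue dose is flat, nothing elsewhere in the protocol scales it, and the eligible population includes infants. Followed literally, it gives 100 mg/kg/day at 10 kg, more below that weight, and 50 mg/kg/day at 20 kg. The wider range, about 143 down to 17 mg/kg/day, rests on assumed weights of 7 and 60 kg.

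The textual finding and the arithmetic are certain. The clinical consequence is not quantified, because the documents give no reference dose. The point should be fixed, but it does not threaten the trial's conclusions.

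**What to change.** In Section 9.1.3, replace the flat amount with: *[X] mg/kg/day, based on the most recent recorded weight, not to exceed 1 gram per day*. The clinical team sets X. This is the per-kg-with-maximum format already used for the peri-infusion steroid in Section 9.1.2.1.

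The cap takes over at weights of 1000/X kg and above, so the present dose is kept for larger boys and lowered for smaller ones. If 1 gram was always meant as a ceiling, the edit simply says so.

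Weight is already recorded at screening, at Day -1 and at the clinic visits from Day 7, so no new measurement is needed. The cost is one line of wording in a protocol amendment, with no effect on visits, endpoints, sample size or analysis.

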#### 9.1.3.1 Day 1

The following assessments will occur at this visit:

- Medical history
- Concomitant Medications
- Adverse Events
- Physical Exam
- Vital Signs (blood pressure, heart rate, respiratory rate, and temperature)

The following blood lab work will occur at this visit:

- Complete blood cell count (CBC) and differential, platelets
- Aspartate aminotransferase (AST)/alanine transaminase (ALT)
- Gamma-glutamyl transpeptidase (GGT)\*
- A Comprehensive Metabolic Panel (CMP) that includes:
  - o Albumin/Serum total protein

- Serum total bilirubin
- Electrolytes
- o Calcium
- o Creatinine/Blood Urea Nitrogen (BUN)
- Serum glucose
- Alkaline phosphatase
- Prothrombin time (PT)/activated partial thromboplastin time (PTT)/INR
- Creatine kinase (CK)
- Direct Bilirubin
- Blood for vector shedding studies (see Section 10.4 for details)

The following urine lab work will occur at this visit:

- Urinalysis
- Urine for biobanking
- Urine for vector shedding studies (see Section 10.4 for details)

The following additional samples will be collected for vector shedding studies (see Section 10.4 for details):

- Saliva
- Feces

The following procedures will occur at this visit:

Picture of Injection Site

#### 9.1.3.2 Day 2

On the second day after gene transfer (Day 2) the subject will be discharged from the hospital following approval from by a study team doctor.

The following assessments will occur at this visit:

- Medical history
- Concomitant Medications
- Adverse Events
- Physical Exam
- Vital Signs (blood pressure, heart rate, respiratory rate, and temperature)

Blood will be collected for vector shedding studies (see Section 10.4 for details):

The following urine lab work will occur at this visit:

- Urine for biobanking
- Urine for vector shedding studies (see Section 10.4 for details)

\* For subjects taking drugs that potentially induce GGT synthesis through the cytochrome P450 system, the clinically significant range will be estimated starting at two times the levels obtained from the baseline screening test and up.

The following additional samples will be collected for vector shedding studies (see Section 10.4 for details):

- Saliva
- Feces

